1. REPORTING & ANALYSIS PLAN SYNOPSIS

Overview	Key Elements of the RAP
Purpose	
 • The purpose of this RAP is to describe the planned analyses and output to be included in the Clinical Study Report for Protocol GlaxoSmithKline Document Number 2015N241692_00 • The planned analyses and output to be included in Clinical Pharmacology Study Report for Protocol 201499. This RAP is intended to describe the pharmacodynamic, biomarker, safety and tolerability analyses required for the study which will be provided to the study team members to convey the content of the reporting efforts, specifically Statistical Analysis Complete (SAC).
Protocol	
 • Reporting and Analysis Plan is based on original protocol (Dated: [12-JAN-2016]) for study 201499 [GlaxoSmithKline Document Number: 2015N241692_00]
Primary Objective / Endpoint	
To characterise the fraction of exhaled nitric oxide (FeNO) time profile following repeat administration of fluticasone furoate/vilanterol (FF/VI) 100/25mcg combination in comparison with placebo in subjects with asthma as measured by :
 
 • Change from baseline FeNO over time following the cessation of repeat dose treatment with FF/VI.
Secondary Objective/ Endpoint	
Change in FeNO over the treatment period following repeat administration of FF/VI 100/25mcg combination in comparison with placebo in subjects with asthma measured by:
 
 • Change from baseline FeNO over the FF/VI treatment period. 
To determine the Peak Expiratory Flow (PEF) during and following repeat administration of FF/VI 100/25mcg combination in comparison with placebo in subjects with asthma measured by:
 
 • Measurement of PEF during treatment and following cessation of repeat dose treatment with FF/VI. 
To determine forced expiratory volume in 1 second (FEV1) following repeat administration of FF/VI 100/25mcg combination in comparison with placebo in subjects with asthma as measured by:
 
 • Measurement of FEV1 pre-treatment and for up to 7 days after cessation of repeat dose treatment with FF/VI.

Overview	Key Elements of the RAP
Exploratory Objective / Endpoint	
To investigate the effect of repeat administration of FF/VI 100/25mcg combination on exploratory biomarkers, including but not limited to, blood eosinophil levels and serum periostin levels, in comparison with placebo in subjects with asthma as measured by:
 
 • Measurement of exploratory biomarkers, including but not limited to, blood eosinophil and serum periostin levels at baseline, and at various time points after cessation of repeat dose treatment with FF/VI
Study Design	
Randomised, double blind, placebo-controlled, two-period, crossover repeat dose study in adult subjects with asthma.
 
Approximately twenty eight adult asthmatic subjects will be enrolled to ensure 24 subjects complete dosing and critical assessments for both treatment periods.
 
Each subject will participate in two treatment periods of 14 (+ 2 days). FF/VI 100/25mcg will be received once daily (AM dosing) in one period and placebo (AM dosing) will be administered in the other period. At the end of each treatment period, there will be a monitoring period of 21 days. Following the 21 day monitoring period following treatment period 1, there may be a period of up to a further 4 weeks before the subjects start treatment period 2.

Planned Analyses	
 • No interim analysis is planned. • The final planned analyses will be performed after database freeze has been declared.
Analysis Population	
 • All Subjects Population comprise of all subjects randomised to treatment who received at least one dose of study medication • Pharmacodynamic Population comprise of all Subjects in the 'All Subjects' population who had at least one PD assessment
Hypothesis	
No formal hypothesis will be tested, an estimation approach will be adopted to address the primary objective. A point estimate and corresponding 95% CI will be constructed for the treatment ratio of test treatment, $\mu(\text{test})$ and reference treatment, $\mu(\text{reference})$, where FF/VI 100/25mcg is the test treatment and placebo the reference treatment

Primary Analyses	
FeNO, change from baseline ratio will be formally analysed following log_e-transformation. A mixed effects repeated measures model will be fitted with fixed effect terms for period, treatment, day, time, (period-level baseline)*day*time interaction term, treatment*day*time interaction term, period-level baseline and subject-level baseline. Day*time interaction term will be fitted as repeated measure. FeNO will be log_e-transformed prior to deriving subject-level baseline and period-level baseline.

Overview	Key Elements of the RAP
Secondary Analyses	FeNO change from baseline ratio during treatment and FEV1 will be analysed similarly to the primary FeNO endpoint. FEV1 will not be log-transformed prior to analysis. PEF will be summarised.
Safety Analyses	Safety data will be summarized
Biomarker Analyses	Exploratory endpoints of biomarkers will be summarized

2. SUMMARY OF KEY PROTOCOL INFORMATION

2.1. Changes to the Protocol Defined Statistical Analysis Plan

There were no changes or deviations to the originally planned statistical analysis specified in the protocol [Dated: 12-JAN-2016].

2.2. Study Objective(s) and Endpoint(s)

Objectives	Endpoints
Primary (Pharmacodynamic)	Primary (Pharmacodynamic)
To characterise the fraction of exhaled nitric oxide (FeNO) time profile following repeat administration of fluticasone furoate/vilanterol (FF/VI) 100/25mcg combination in comparison with placebo in subjects with asthma.	Change from baseline FeNO over time following the cessation of repeat dose treatment with FF/VI.
Secondary (Pharmacodynamic)	Secondary (Pharmacodynamic)
Change in FeNO over the treatment period following repeat administration of FF/VI 100/25mcg combination in comparison with placebo in subjects with asthma.	Change from baseline FeNO over the FF/VI treatment period
To determine the Peak Expiratory Flow (PEF) during and following repeat administration of FF/VI 100/25mcg combination in comparison with placebo in subjects with asthma.	Measurement of PEF during treatment and following cessation of repeat dose treatment with FF/VI.
To determine FEV1 following repeat administration of FF/VI 100/25mcg combination in comparison with placebo in subjects with asthma	Measurement of FEV1 pre-treatment and for up to 7 days after cessation of repeat dose treatment with FF/VI

Objectives	Endpoints
Exploratory (Biomarker)	Exploratory (Biomarker)
To investigate the effect of repeat administration of FF/VI 100/25mcg combination on exploratory biomarkers, including but not limited to, blood eosinophil levels and serum periostin levels, in comparison with placebo in subjects with asthma	Measurement of exploratory biomarkers, including but not limited to, blood eosinophil and serum periostin levels at baseline, and at various time points after cessation of repeat dose treatment with FF/VI

2.3. Study Design

Overview of Study Design and Key Features	

The diagram illustrates the study design timeline. It starts with a 'Run in (SABA only)' phase. Treatment Period 1 begins on Day 1 with FF/VI 100/25 for 14 days, followed by a 21-day Washout period. Treatment Period 2 is identical to Period 1, separated by a crossover period. Clinical units and measurements are indicated by 'X' marks and arrows.
	
Design Features	This study is a randomized, double-blind, placebo-controlled, two-period, crossover repeat dose study to characterise the exhaled nitric oxide time profile as a biomarker of airway inflammation in adult asthmatics.
Dosing	Each subject will participate in two treatment periods of 14 (+/- 2 days). FF/VI 100/25 mcg will be received once daily (AM dosing) in one period and placebo (AM dosing) will be administered in the other period. At the end of each treatment period, there will be a monitoring period of 21 days. Following the 21 day monitoring period following treatment period 1, there may be a period of up to a further 4 weeks before the subjects start treatment period 2. Total duration for each subject (from screening to follow-up) will be a minimum of 11 weeks, with a maximum of up to 21 weeks, depending on the screening period and the time period between Treatment Periods 1 and 2

Overview of Study Design and Key Features	
Treatment Assignment	Subjects will be randomized to one of two sequences AB or BA. Where, A=Placebo and B=FF/VI 100/25mcg. Subjects will be administered the first treatment in the sequence in the first period and the second treatment in the sequence in the second period.

2.4. Statistical Hypotheses

No formal hypothesis will be tested, an estimation approach will be adopted to address the primary objective. A point estimate and corresponding 95% CI will be constructed for the treatment ratio of test treatment, μ (test) and reference treatment, μ (reference), where, FF/VI 100/25mcg is the test treatment and placebo the reference treatment.

3. PLANNED ANALYSES

3.1. Interim Analyses

No interim analysis is planned.

3.2. Final Analyses

Analysis	Details
Final Analyses	The final planned analyses will be performed after all subjects have completed the study and after database freeze/unblinding. See Section 6 Section 9 for all final planned analyses for this study.

The final planned primary analyses will be performed after the completion of the following sequential steps:

1. All subjects have completed the study as defined in the protocol
2. All required database cleaning activities have been completed and final database release has been declared by Data Management.
3. All protocol deviations have been confirmed
4. All criteria for unblinding the randomisation codes have been met.
5. Randomisation codes have been distributed according to RandAll NG procedures.
6. Database freeze has been declared by Data Management.

4. ANALYSIS POPULATIONS

Population	Definition / Criteria	Analyses/Endpoint(s) Evaluated
Screened Subjects	
 Comprise of all subjects who attended the screening visit 	
 Study Population
All Subjects Population	
 Comprise of all subjects randomised to treatment who received at least one dose of study medication. 	
 Study Population Biomarker Safety
Pharmacodynamic Population	
 Subjects in the 'All Subjects' population who had at least one PD assessment 	
 Pharmacodynamic 
 FeNO FEV1 PEF

NOTES: Please refer to Appendix 10 which details the population to be used for each display being generated.

4.1. Protocol Deviations

- Protocol deviations will be tracked by the study team throughout the conduct of the study in accordance with the Protocol Deviation Management Plan.
 - Data will be reviewed by the study team prior to database release to ensure all important deviations are captured and categorised on the protocol deviations dataset.
 - The SI dataset will include all protocol deviations, the analysis dataset will include only important protocol deviations. The analysis dataset will be used for the listing and summary of important protocol deviations.
- A separate listing of all inclusion/exclusion criteria deviations will also be provided.
- The study endpoints will be reported using the populations detailed in Section 4 of this document regardless of whether the subjects deviate from the protocol.
- If there are subjects with protocol deviations that may potentially impact the PD endpoints which needs to be confirmed prior to unblinding, exploratory sensitivity analyses may be considered. If further sensitivity analyses of the data are produced, they will be detailed in the clinical study report.

5. CONSIDERATIONS FOR DATA ANALYSES AND DATA HANDLING CONVENTIONS

Table 1 provides an overview of appendices within the RAP for outlining general considerations for data analyses and data handling conventions.

Table 1 Overview of Appendices

Section	Component
11.1	Appendix 1: Protocol Deviation Management and Definitions for Per Protocol Population
11.2	Appendix 2: Data Management
11.3	Appendix 3: Time and Event
11.4	Appendix 4: Treatment States and Phases
11.5	Appendix 5: Data Display Standards & Handling Conventions
11.6	Appendix 6: Derived and Transformed Data
11.7	Appendix 7: Premature Withdrawals & Handling of Missing Data
11.8	Appendix 8: Model Checking and Diagnostics for Statistical Analyses
11.9	Appendix 9: Abbreviations & Trade Marks
11.10	Appendix 10: List of Data Displays
11.11	Appendix 11: Example Mock Shells for Data Displays

6. STUDY POPULATION ANALYSES

6.1. Overview of Planned Analyses

The study population analyses will be based on the “All Subjects” population, unless otherwise specified.

Table 2 provides an overview of the planned study population analyses, with full details of data displays being presented in Appendix 10: List of Data Displays.

Table 2 Overview of Planned Study Population Analyses

Endpoint	Data Displays Generated		
	Table	Figure	Listing
Subject Disposition			
Subject Disposition for the Subject Conclusion Record	Y		
Reasons for Subject Withdrawal			Y
Screening Status and Reasons for Screen Failure	Y		Y
Subjects Enrolled by Country and Site ID	Y		
Subjects for Whom the Treatment Blind was Broken			Y
Planned and Actual Treatments			Y
Protocol Deviations			
Important Protocol Deviations	Y		Y
Subjects with Inclusion/Exclusion Criteria Deviations			Y
Populations Analysed			
Study Populations	Y		
Subjects Excluded from Any Population			Y
Demographic and Baseline Characteristics			
Demographic Characteristics	Y ^[1]		Y
Age Ranges	Y		
Race and Racial Combinations	Y		Y ^[2]
Prior and Concomitant Medications			
Current & Past Medical Conditions			Y
Concomitant Medications			Y
Exposure			
Exposure to Study Treatment	Y		Y

NOTES :

- Y = Yes display generated.
- [1] Conditional Display for PD Population.
- [2] Listing of race.

7. PRIMARY STATISTICAL ANALYSES

7.1. Pharmacodynamic Analyses

Statistical Analysis of Pharmacodynamic endpoints will be performed by or under the direct auspices of, Clinical Statistics, GlaxoSmithKline.

7.1.1. Overview of Planned Pharmacodynamic Analyses

The primary Pharmacodynamic analyses will be based on the “Pharmacodynamic (PD)” population, unless otherwise specified.

Table 3 provides an overview of the planned Pharmacodynamic analyses, with full details of data displays being presented in Appendix 10: List of Data Displays.

Table 3 Overview of Planned Pharmacodynamic Analyses

Endpoint	Absolute				Change from Baseline			
	Summary		Individual		Summary		Individual	
	T	F	F	L	T	F	F	L
FeNo	Y			Y	Y			

Endpoint	Log _e transformed							
	Stats Analysis			Summary			Individual	
	T	F	L	T	F	L	F	L
FeNO	Y	Y	Y	Y			Y	Y

NOTES:

- T = Table, F = Figures, L = Listings, Y = Yes display generated.
- Summary = Represents TF related to any summaries (descriptive statistics) of the observed raw data.
Individual = Represents FL related to any displays of individual subject observed raw data.

7.1.1.1. Statistical Analysis of Pharmacodynamic Parameters

For the PD parameter of FeNO, the following summary statistics will be calculated and tabulated by treatment:

- **Untransformed Data :** N, n, arithmetic mean, 95% confidence interval (CI) for the arithmetic mean, SD, median, minimum, maximum
- **Log_e-transformed Data:** Geometric mean, 95% CI for the geometric mean, SD of log_e-transformed data and %CVb

7.1.2. Planned Primary Pharmacodynamic Statistical Analyses

Primary Statistical Analyses
Endpoint

 Change from baseline ratio of \log_e transformed FeNO over time following the cessation of repeat dose treatment with FF/VI.
Model Specification

Endpoints will be statistically analysed using a mixed models repeated measures (MMRM) model.
 
Terms fitted in the MMRM model will include:
 
Fixed effect terms: Period, Treatment, Day, Time, Period-level baseline*Day*Time interaction term, Treatment*Day*Time interaction term, Period-level baseline and Subject-level baseline.
 
Repeated: Day*Time interaction term.
 
Note: FeNO will be \log_e-transformed prior to deriving subject-level baseline and period-level baseline.

Model Checking & Diagnostics

 Refer to Appendix 8: Model Checking and Diagnostics will be performed for mentioned Statistical Analyses as required.
Model Results Presentation

 Point estimates and their associated 95% confidence intervals will be constructed for the difference [FF/VI 100/25mcg] – [Placebo] at each timepoint (AM and PM i.e. pre-dose & 12 hours) on each day. The point estimates and their associated 95% confidence intervals will then be back-transformed to provide point estimates and 95% confidence intervals for the ratios, [FF/VI 100/25mcg]/[Placebo] for each day and AM/PM timepoint. Estimates of within-subject variability for FeNO will also be provided, where $CV_w(\%) = \text{SQRT}(\exp(\text{MSE}) - 1) \times 100$ and MSE is the residual mean squared error from the model. CV_w represents a pooled measure of within-subject variability across the regimens FF/VI 100/25mcg, Placebo and timepoints.

8. SECONDARY STATISTICAL ANALYSES

8.1. Pharmacodynamic Analyses

8.1.1. Overview of Planned Pharmacodynamic Analyses

The secondary Pharmacodynamic analyses will be based on the “Pharmacodynamic (PD)” population, unless otherwise specified.

[Table 4](#) provides an overview of the planned Pharmacodynamic analyses, with further details of data displays being presented in [Appendix 10](#): List of Data Displays.

Table 4 Overview of Planned Pharmacodynamic Analyses

Endpoint	Absolute				Change from Baseline							
	Summary		Individual		Stats Analysis			Summary		Individual		
	T	F	F	L	T	F	L	T	F	F	L	
FeNO ^[1]					Y	Y	Y					
FEV1	Y			Y	Y	Y	Y	Y				
PEF	Y			Y								

NOTES:

[1] FeNO will be \log_e transformed prior to analysis.

- T = Table, F = Figures, L = Listings, Y = Yes display generated.
- Summary = Represents TF related to any summaries (descriptive statistics) of the observed raw data.
Individual = Represents FL related to any displays of individual subject observed raw data.

8.1.2. Planned Secondary Pharmacodynamic Statistical Analyses

Secondary Statistical Analyses
Endpoint

 • Change from baseline ratio of \log_e transformed FeNO during treatment with FF/VI.
Model Specification

Endpoints will be statistically analysed using a mixed models repeated measures (MMRM) model.
 
Terms fitted in the MMRM model will include: Fixed effect terms: Period, Treatment, Day, Time, Period-level baseline*Day*Time interaction term, Treatment*Day*Time interaction term, Period-level baseline and Subject-level baseline. Repeated: Day*Time interaction term.
 
Note: FeNO will be \log_e-transformed prior to deriving subject-level baseline and period-level baseline.

Model Checking & Diagnostics

 • Refer to Appendix 8: Model Checking and Diagnostics will be performed for mentioned Statistical Analyses as required.
Model Results Presentation

 • Point estimates and their associated 95% confidence intervals will be constructed for the difference [FF/VI 100/25mcg] – [Placebo] at each timepoint (AM/PM i.e. pre-dose & 12 hours) on each day. • Estimates of within-subject variability for FeNO will also be provided, where $CV_w(\%) = \text{SQRT}(\exp(\text{MSE}) - 1) \times 100$ and MSE is the residual mean squared error from the model. CV_w represents a pooled measure of within-subject variability across the regimens FF/VI 100/25mcg, Placebo and timepoints.
Endpoint

 • Change from baseline of FEV1 during treatment with FF/VI.

Secondary Statistical Analyses
Model Specification

Endpoints will be statistically analysed using a mixed models repeated measures (MMRM) model.
 
Terms fitted in the MMRM model will include:
 
Fixed effect terms: Period, Treatment, Day, Time, Period-level baseline*Day*Time interaction term, Treatment*Day*Time interaction term, Period-level baseline and Subject-level baseline.
 
 • Repeated: Day*Time interaction term.
Model Checking & Diagnostics

 • Refer to Appendix 8: Model Checking and Diagnostics will be performed for mentioned Statistical Analyses as required.
Model Results Presentation

 • Point estimates and their associated 95% confidence intervals will be constructed for the difference [FF/VI 100/25mcg] – [Placebo] at each timepoint (AM/PM i.e. pre-dose & 12 hours) on each day. • Estimates of within-subject variability for FEV1 will also be provided, where $CVw(\%) = \text{SQRT}(\exp(\text{MSE}) - 1) \times 100$ and MSE is the residual mean squared error from the model. CVw represents a pooled measure of within-subject variability across the regimens FF/VI 100/25mcg, Placebo and timepoints.

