3. OBJECTIVE(S) AND ENDPOINT(S)

| Objectives | Endpoints |
|--|--|
| Primary | |
| 
 To characterise the fraction of exhaled nitric oxide (FeNO) time profile following repeat administration of fluticasone furoate/vilanterol (FF/VI) 100/25mcg combination in comparison with placebo in subjects with asthma. | 
 Change from baseline FeNO over time following the cessation of repeat dose treatment with FF/VI. |
| Secondary | |
| 
 Change in FeNO over the treatment period following repeat administration of FF/VI 100/25mcg combination in comparison with placebo in subjects with asthma. To determine the Peak Expiratory Flow (PEF) during and following repeat administration of FF/VI 100/25mcg combination in comparison with placebo in subjects with asthma. To determine FEV₁ following repeat administration of FF/VI 100/25mcg combination in comparison with placebo in subjects with asthma | 
 Change from baseline FeNO over the FF/VI treatment period. Measurement of PEF during treatment and following cessation of repeat dose treatment with FF/VI. Measurement of FEV₁ pre-treatment and for up to 7 days after cessation of repeat dose treatment with FF/VI. |
| Exploratory | |
| 
 To investigate the effect of repeat administration of FF/VI 100/25mcg combination on exploratory biomarkers, including but not limited to, blood eosinophil levels and serum periostin levels, in comparison with placebo in subjects with asthma. | 
 Measurement of exploratory biomarkers, including but not limited to, blood eosinophil and serum periostin levels at baseline, and at various time points after cessation of repeat dose treatment with FF/VI. |

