4. STUDY DESIGN

4.1. Overall Design

This study will be a randomised, double blind, placebo-controlled, two-period, crossover repeat dose study in adult subjects with asthma.

Following screening, subjects will provide AM and PM FeNO and PEF data from Day -7 of Treatment Period 1. The Day -7 AM FeNO readings will be used to confirm eligibility (FeNO >40ppb). On Day 1, pre-treatment (AM) FeNO, FEV₁ and PEF readings will be used as baseline for Treatment Period 1. Subjects will then receive FF/VI 100/25 or placebo once daily (AM) for 14 (\pm 2) days. All treatments will be taken at the same time of day (within \pm 2 hours of the treatment on Day 1).

FeNO will be measured by the subjects AM (pre-dose) and PM for 14 days during each treatment period. On Day 14, FEV₁ and FeNO will be recorded before the final dose of FF/VI or placebo.

FeNO (AM and PM) will be measured for 21 days after the end of treatment (up to Day 35 for each of the two treatment periods). This will be as an in-patient on Days 14 to 19. All FeNO (out-patient and in clinic) measurements will be obtained using the same FeNO meter for each subject.

FEV₁ will be recorded AM and PM (i.e. every 12 hours) as an in-patient on Days 14 to 19. Subjects will then be discharged before returning 2 days later (on Day 21) for a further measurement of FEV₁ (168 hours post-treatment). An FEV₁ measurement will also be performed on Day 35.

Up to 4 weeks after the final assessment is collected on Day 35 of Treatment Period 1, subjects will then be crossed over to the alternative treatment. Baseline FEV₁, PEF and FeNO values will be collected pre-treatment in the morning on Day 1: these will be the baseline values for Treatment Period 2. Subjects will then receive FF/VI 100/25 or placebo once daily (AM) for 14 (\pm 2) days. The second treatment period procedures will be identical to the first treatment period.

[figure not shown]
A single measurement of FeNO will be collected according to ATS/ERS guidelines at each time point, using a NIOX Vero device with electronic data capture. Appropriate dietary and/or lifestyle restrictions will be applied. The order of assessments collected in the clinic will be: FeNO, FEV₁, and then PEF. When the subjects are at home, FeNO will be collected before the PEF measurements. FEV₁ measurements taken within 6 hours of SABA use will not be analysed.

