11.3. Appendix 3: Time & Events

Procedure	Screening (up to 42 days prior to Day 1)	Study Day (each treatment period)						Follow-up (Days 35-42) ¹²	Notes
		Day -7 (start of run-in) ¹	Day 1	Days 2-13	Days 14-19	Day 21	Day 35		
Out-patient visit to the unit	X	X	X			X	X	X	¹ Day -7 is the start of the one week run-in period and therefore this visit and the assessments on this day only apply to Treatment Period 1
Admission to the unit					X				
Informed consent	X								
Inhaler, PEF meter and FeNO device practice	X								
Inclusion and exclusion criteria/eligibility review	X	X	X						
Demography	X								
Full physical exam including height and weight	X								
Medical history (includes substance usage [and family history of premature CV disease])	X								Substances: [Drugs, Alcohol, tobacco and caffeine]
Past and current medical conditions [including cardiovascular medical history]	X								

CONFIDENTIAL

201499

Procedure	Screening (up to 42 days prior to Day 1)	Study Day (each treatment period)						Follow-up (Days 35-42) ¹²	Notes
		Day -7 (start of run-in) ¹	Day 1	Days 2-13	Days 14-19	Day 21	Day 35		
Urine pregnancy test (WCBP)	X		X ²			X		X	² Collected pre-dose
Vital signs	X								
Set up PEF and FeNO monitoring		X							
Study Treatment			X ³		X ⁴				³ Dosing every morning; dosing in the unit on Days 1 and 14 and at home on Days 2-13 ⁴ Dosing on the morning of Day 14 only
Exploratory biomarker sampling ⁵		X			X	X	X		⁵ These measurements are taken at baseline (Day -7), at the end of treatment (Day 15), on Day 21 and on Day 35.
FEV ₁ readings ⁶	X		X ⁷		X ⁸	X ⁹			⁶ Measured in the unit only ⁷ Taken pre-dose ⁸ Collected AM (pre-dose on Day 14) and PM ⁹ Collected AM only
FeNO assessment ¹⁰	X	←-----→							¹⁰ Start of collection 7 days before Day 1 (Day -7), then collected every day AM and PM through to Day 35 of each treatment period.

CONFIDENTIAL

201499

Procedure	Screening (up to 42 days prior to Day 1)	Study Day (each treatment period)						Follow-up (Days 35-42) ¹²	Notes
		Day -7 (start of run-in) ¹	Day 1	Days 2-13	Days 14-19	Day 21	Day 35		
PEF ¹¹		←=====→							¹¹ Collected AM and PM every day from Day -7 through to Day 35 for Treatment Period 1, and from Day 1 through to follow up for Treatment Period 2.
AE/SAE review		←=====→							
Concomitant medication review		←=====→							¹² Follow up visit only after Treatment period 2. The follow-up visit can be combined with the Day 35 visit for Treatment Period 2.

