11.10.5. Pharmacodynamic Tables

Efficacy: Tables					
No.	Population	Example Shell	Title	Programming Notes	Deliverable [Priority]
Pharmacodynamic Parameters					
2.1.	PD	LB1	Summary of Exhaled Nitric Oxide Data	Parameter with units, both untransformed and transformed	Headline [1] SAC [2]
2.2.	PD	LB1	Summary of Change from Baseline Exhaled Nitric Oxide Data	Parameter with units for untransformed data	SAC [2]
2.3.	PD	LB1	Summary of Ratio from Baseline Exhaled Nitric Oxide Data	Parameter with units for transformed data	Headline [1] SAC [2]
2.4.	PD	PD_T1	Summary of Repeated Measures Statistical Analysis of Ratio from Baseline Exhaled Nitric Oxide Data after cessation of repeat dose of treatment		Headline [1] SAC [2]
2.5.	PD	PD_T1	Summary of Repeated Measures Statistical Analysis of Ratio from Baseline Exhaled Nitric Oxide Data		SAC [2]
2.6.	PD	LB1	Summary of Spirometry data		SAC [2]
2.7.	PD	LB1	Summary of Change from Baseline in Spirometry data		SAC [2]
2.8.	PD	PD_T1	Summary of Repeated Measures Statistical Analysis of Change from Baseline FEV1 Data		SAC [2]

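### SAP 8.1.2 sets the modelled FEV1 window as on-treatment, which contradicts the FEV1 endpoint (pre-treatment and the 7 days after cessation) and is not declared as a change

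*SAP*

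**What the plan says.** - **Model text.** The FEV1 entry in SAP Section 8.1.2 states the endpoint as "Change from baseline of FEV1 during treatment with FF/VI". It specifies an MMRM with Day, Time, treatment-by-day-by-time and baseline-by-day-by-time terms, and asks for treatment differences "at each timepoint (AM/PM i.e. pre-dose & 12 hours) on each day".
- **Endpoint text.** SAP Section 2.2 defines the endpoint as "Measurement of FEV1 pre-treatment and for up to 7 days after cessation of repeat dose treatment with FF/VI", and the SAP synopsis agrees. Protocol Section 3 and the protocol synopsis give the same window: "pre-treatment and for up to 7 days after cessation of repeat dose treatment with FF/VI".
- **Declared changes.** SAP Section 2.1 says: "There were no changes or deviations to the originally planned statistical analysis specified in the protocol".
- **Other analysis text.** Protocol Section 9.4.2 and the Secondary Analyses row of the SAP synopsis attach the on-treatment qualifier to FeNO only. They name FEV1 without a window and say it is analysed in a similar way to the primary FeNO endpoint, which SAP Section 7.1.2 defines as post-cessation.
- **Schedule.** FEV1 is "Measured in the unit only" (SAP Section 11.3). It is taken pre-dose on Day 1, AM and PM on Days 14-19 and AM on Day 21. None is scheduled on Days 2-13. The last dose is on the morning of Day 14, after that morning's reading.

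**The concern.** The box that a programmer would work from names a different period from the one the endpoint names. The phrase cannot be passed over as loose wording, because for FeNO the SAP uses *during treatment* (8.1.2) and *following the cessation* (7.1.2) as two separate analysis windows. The FEV1 objective is mainly about the time after dosing stops, and almost all scheduled post-baseline FEV1 readings fall there.

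What is at stake is the modelled FEV1 output: Table 2.8 and Figures 2.5 and 2.6. Their titles state no window, so they do not correct the box. No rule says which SAP section prevails when two disagree.

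**Working it through.** The documents give no precision or sample-size figure for FEV1, so there is no plan figure to reproduce. The check is a count of readings and of estimable model terms.

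**Inputs** (Protocol Sections 4.1 and 7.1; SAP Section 11.3), on the nominal 14-day schedule with the last dose on Day 14 AM = 0 h:
- Day 14 AM, pre-dose: 1 reading
- Day 14 PM, 12 h: 1 reading
- Days 15-19, AM and PM, 24 h to 132 h: 5 × 2 = 10 readings
- Day 21 AM, 168 h: 1 reading

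Total post-baseline readings per period up to 168 h: 1 + 1 + 10 + 1 = 13. After the last dose: 13 − 1 = 12.

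Day 19 PM is uncertain. After the in-patient stay on Days 14 to 19, Protocol Section 4.1 says "Subjects will then be discharged before returning 2 days later (on Day 21"), which puts discharge on Day 19 without saying whether the evening reading comes first. Without it the totals are 12 and 11.

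**Where does *during treatment* end?** SAP 8.1.2 does not say, so three cut-offs are shown:
1. At the Day 14 AM dose.
2. At the end of Day 14. Protocol 4.1 counts AM and PM FeNO over 14 days as within the treatment period, and SAP 11.4.1 (written for adverse events) runs on-treatment status through the treatment stop date.
3. At 24 h after the last dose, one dosing interval.

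**Model rank.** For k readings per period, the fixed effects in the FEV1 box span treatment by day by time (2k), baseline by day by time (k), period (1) and subject-level baseline (1). The rank is therefore 2k + k + 1 + 1 = 3k + 2. A numerical check with 24 subjects, sequences AB and BA and simulated baselines gave the same values.

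| Window | Readings in window | Share of 13 | Share of 12 (no Day 19 PM) | Rank | Post-cessation differences omitted |
|---|---|---|---|---|---|
| Ends at Day 14 AM dose | 1 | 7.7% | 8.3% | 5 | 12 of 12 (11 of 11) |
| Includes Day 14 PM | 2 | 15.4% | 16.7% | 8 | 11 of 12 (10 of 11) |
| To 24 h after last dose | 3 | 23.1% | 25.0% | 11 | 10 of 12 (9 of 11) |
| Post-cessation readings to 168 h | 12 (11) | – | – | 38 (35) | 0 |

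In the first row the rank of 5 is made up of the intercept, period, treatment and the two baselines, so the Day and Time terms add nothing. In the second and third rows they add 3 and 6. On every reading the box covers a small minority of the scheduled data and at most 2 of the 12 post-cessation time points.

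**The case against.** The strongest reply is that the intended analysis is clear. Protocol 9.4.2 and the SAP synopsis tie FEV1 to the post-cessation primary analysis, SAP 2.2 gives the right window, SAP 2.1 disclaims any change, and Figure 2.5 is titled as a time profile. The FEV1 entry also sits directly under a FeNO entry with the same wording, so a carried-over phrase is the natural explanation. A programmer would probably notice. This largely stands, and it limits the severity. It does not remove the problem, because the similarly-analysed wording lists no time points and whoever noticed would still have to choose them.

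A reader might go further than the documents allow in three ways:
- *The model cannot be fitted over time.* This is true only if the window closes at the Day 14 AM dose. The documents' own usage elsewhere supports counting Day 14 PM as on treatment, and the Day and Time terms then have something to estimate.
- *No post-cessation FEV1 difference would be estimated.* This holds only on the same narrowest cut-off. On the wider ones, one or two such differences remain.
- *The sponsor has changed the endpoint without saying so.* The declaration in SAP 2.1 and the other analysis text point to a drafting slip.

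It is also fair that this is one secondary endpoint in a study that estimates and does not test.

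**Conclusion.** The contradiction is real and lies in the operative model text. On any of the three cut-offs, the window as written would leave at least 10 of the 12 post-cessation FEV1 treatment differences (9 of 11 without Day 19 PM) out of Table 2.8 and Figures 2.5 and 2.6. It does not show that data would in fact be dropped.

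Descriptive FEV1 outputs carry no such limit: Tables 2.6 and 2.7 (the latter titled "Summary of Change from Baseline in Spirometry data"), Figure 2.4 and Listing 21. The primary FeNO analysis and the sample size are also untouched. Severity is low to moderate: worth correcting before unblinding because the correction is nearly free.

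The counts assume the nominal 14-day treatment period and stop at 168 h. Day 35 lies outside the 7-day endpoint and is not counted.

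**What to change.** In the FEV1 box of SAP 8.1.2, restate the endpoint as FEV1 change from baseline over the 7 days (168 h) after dosing stops, and fit the MMRM over the scheduled post-cessation readings, Day 14 PM to Day 21 AM. List the modelled time points in the same box and settle three that the documents leave open:
- whether Day 14 AM pre-dose enters the model;
- whether Day 19 PM is collected and modelled;
- whether Day 35 is modelled. Protocol Sections 4.1 and 7.1 schedule an FEV1 reading then, but the SAP Time and Events table does not show it.

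If a restricted on-treatment window was intended, declare it in SAP 2.1 with a reason.

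The cost is one sentence and a one-line list of time points, with no new data and no change to the planned displays.
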